3 STUDY DESIGN

3.1 General Study Design

This study is an open-label extension study of the safety and tolerability of pimavanserin for the treatment of agitation and aggression in subjects with probable AD. This study will be conducted as a 52-week, open-label, flexible-dose extension of Study ACP-103-032. Subjects in Study ACP-103-033 must have completed ACP-103-032 and must meet eligibility criteria.

Study ACP-103-033 subjects must be consented prior to the final procedures being performed for Study ACP-103-032 at Week 12. Procedures from the Week 12 visit of Study ACP-103-032 will be carried over to the ACP-103-033 study to be included as Baseline information and this visit will be considered the Baseline Visit (Visit 1) of the ACP-103-033 study.

All subjects will receive once daily (QD) doses of pimavanserin (active study drug) over 52 weeks of treatment, starting with 20 mg a day. At the Week 2 visit, the pimavanserin 20 mg dose may be increased to 34 mg a day based on the Investigator's assessment of clinical response. The Investigator may then adjust the dose from 20 mg to 34 mg or from

34 mg to 20 mg at any visit based on clinical response. A dose change at a time other than at a scheduled clinic visit will require an unscheduled visit to dispense the appropriate dose of study drug. Unscheduled clinic visits may occur as needed.

The duration of participation for individual subjects will be up to approximately 56 weeks: each subject will participate in a 52-week open-label treatment period followed by an approximately 30-day safety follow-up period. The end of the clinical trial will be when the last subject completes the last scheduled assessment (i.e., 30-day follow-up).

3.2 Schedule of Assessments

The schedule of events and assessments for the study is presented in [Table 1](#).

Table 1 Schedule of Assessments

Visit Number	Treatment Period											Follow-Up
	Baseline ^b 1	2	3	4	5	6	7	8	9	(EOS/ET) 10	Unscheduled	11
Visit Week ^a	0	Week 2	Week 4	Week 8	Week 12	Week 20	Week 28	Week 36	Week 44	Week 52		Week 56
Allowable visit window (# days)		±3	±3	±3	±3	±7	±7	±7	±7	+7		+7
Informed consent ^b	X											
Inclusion/exclusion criteria	X											
Physical examination	X				X					X		
Vital signs	X	X	X	X	X	X	X	X	X	X	X	
Weight	X	X	X	X	X	X	X	X	X	X		
ECG ^c	X		X		X		X			X		
Clinical laboratory tests	X		X		X		X			X		
Pregnancy test ^d	X		X		X	X	X	X	X	X		
CMAI	X	X	X	X	X	X	X	X	X	X	X ^h	
ZBI	X	X	X	X	X	X	X	X	X	X		
NPI-C (all domains)	X				X		X			X		
NPI-C (agitation and aggression domains only)		X	X	X								
MMSE	X		X	X	X	X	X	X	X	X		
KSS	X				X		X			X		
mADCS-CGIC	X	X	X	X	X	X	X	X	X	X	X ^h	
ADCS-ADL	X				X		X			X		
Assessment of concomitant medications/procedures	X	X	X	X	X	X	X	X	X	X	X	X
Assessment of AEs ^e	X	X	X	X	X	X	X	X	X	X	X	X
GCAS	X	X	X	X	X	X	X	X	X	X	X	X
Dispense study drug ^f	X ^g	X	X	X	X	X	X	X	X		X ^h	
Study drug accountability		X	X	X	X	X	X	X	X	X	X ^h	

Abbreviations: ADCS-ADL=Alzheimer's Disease Cooperative Study–Activities of Daily Living; AE(s)=adverse event(s); CMAI=Cohen-Mansfield Agitation Inventory; ECG=electrocardiogram; EOS/ET=end-of-study/early termination; GCAS= Global Clinician Assessment of Suicidality; KSS=Karolinska Sleepiness Scale; mADCS-CGIC=modified Alzheimer's Disease Cooperative Study – Clinical Global Impression of Change; MMSE=Mini-Mental State Examination; NPI-C=Neuropsychiatric Inventory-Clinician rating scale; ZBI=Zarit Burden Interview

- ^a Study visits are designated by weeks and have a ± 3 -day window (Visits 2 through 5), or a ± 7 -day window (Visit 6 through 9), or a +7-day window (Visits 10 and 11) calculated from the Baseline Visit.
- ^b Study ACP-103-033 subjects **must be** consented prior to the final procedures being performed for Study APC-103-032 at Week 12. Procedures from the Week 12 visit of Study ACP-103-032 will be carried over as baseline information, if applicable.
- ^c A single 12-lead ECG can be performed any time before blood sampling or at least 30 minutes after blood sampling during clinic visits.
- ^d A urine pregnancy test should be performed for female study subjects of childbearing potential.
- ^e Any untoward medical occurrence that occurs after the completion of procedures at the Week 12 visit in double-blind Study ACP 103-032 should be recorded as an AE, even if dosing for ACP-103-033 has not begun.
- ^f Study drug will be dispensed to the subject at either scheduled or unscheduled visits.
- ^g Study drug will be dispensed to the subject to take home at the Baseline visit. The subject and their study partner/caregiver will be provided instructions to take the first dose of study drug on the following day.
- ^h To be completed at unscheduled visits where there is a dose change.

3.3 Randomization

Not applicable.

3.4 Blinding

Not applicable.

3.5 Determination of Sample Size

The planned sample size for this study is not based on statistical power but will depend on the number of subjects who complete Study ACP-103-032 and who then transition into this open-label extension study.

Up to approximately 111 male and female subjects with probable AD who have symptoms of agitation and aggression and who have completed Study ACP-103-032 and meet the eligibility criteria for ACP 103-033 will enroll in this study.

4 ANALYSIS SETS

The Safety Analysis Set will include all subjects who received at least 1 dose of open-label study drug. The Safety Analysis Set will be used for all analyses.

5 DATA HANDLING CONVENTIONS

All data collected in the study will be listed.

5.1 General Data Reporting Conventions

For continuous variables, the following summary statistics will be provided: number of subjects, mean, standard error of the mean (SE), standard deviation (SD), minimum, maximum and median. Unless specified otherwise, means, medians, and confidence intervals (CIs) will be presented to one more decimal place than the raw data, and the SDs deviations and SEs will be presented to 2 more decimal places than the raw data. Unless specified otherwise, all confidence intervals will be 2-sided 95% confidence intervals.

For categorical variables, summaries will include the number and percentage of subjects in each category, using the number of subjects with non-missing values as the denominator for the percentages (unless otherwise specified). Categories with zero counts will not have zero percentages displayed. Percentages will be presented with 1 decimal place.

When converting number of days to months, it will be calculated by dividing the number of days by 365.25 and then multiplying by 12. When converting number of days to years, the number of days will be divided by 365.25.

No hypothesis testing is planned. Descriptive summaries of all safety and efficacy endpoints will be provided. All safety and efficacy measures will be summarized for the Safety Analysis Set. Summaries by treatment group according to the original treatment in double-blind Study ACP-103-032 (placebo, pimavanserin 20 mg, and pimavanserin 34 mg) will be provided. All references to double-blind treatment group refer to the initial treatment group in Study ACP-103-032.

For each continuous measure in safety and efficacy analyses, change from Baseline results will be presented in two ways:

1. Using the Baseline from Study ACP-103-033 and reporting the changes across Study ACP-103-033 timepoints;
2. Using the Baseline from Study ACP-103-032 and reporting the changes across the timepoints of both the double-blind Study ACP-103-032 and the open-label Study ACP-103-033.

5.2 Derived Variables

In general, assessment total scores and subscale scores will be derived within the analysis datasets. In the event that total scores and/or subscale scores are also collected on the electronic case report form (eCRF), the derived values will be used for all summaries. Both the raw and derived scores will be presented in listings.

All Baseline assessments that are referred to in the following sections will be carried over from the Week 12 visit of double-blind Study ACP-103-032, where applicable.

5.2.1 Cohen-Mansfield Agitation Inventory Long-form (CMAI)

The CMAI is assessed at Baseline, and Weeks 2, 4, 8, 12, 20, 28, 36, 44, and 52/ET visits.

The CMAI is a 29-item scale designed to systematically assess agitation, rated on a 7-point (1-7) scale of frequency (1 = Never; 2 = Less than once a week; 3 = Once or twice a week; 4 = Several times a week; 5 = Once or twice a day; 6 = Several times a day; 7 = Several times an hour). Subjects are rated by their primary caregiver regarding the frequency with which they manifest physically aggressive, physically non-aggressive, and verbally agitated behaviors. The CMAI in this study is to be completed by interview of the caregiver. Ratings are inclusive of the 2 or 4 weeks prior to the administration of the scale.

In addition to the 7-point frequency scale, there are two other options for rating the behavior: 1) “8 - would occur if not prevented” (e.g., a person is physically restrained so he/she cannot pace), and 2) “9 - not applicable” (e.g., a non-verbal resident not being able to repeat sentences or questions, or a person who cannot walk or move a wheelchair not being able to pace, an amputated person not being able to kick). These two ratings are used only if the

behavior really has never occurred in the past two weeks. If it has occurred, then the 1-7 point frequency scale should be used. These ratings of 8 and 9 are not included in the CMAI total score calculation. The CMAI has a range of 29-203 points, with higher scores indicating more severe agitation symptoms. If there are less than 6 missing items then the total score will be imputed by replacing each missing item with the mean (rounded to the nearest integer) of the non-missing values for that subject and timepoint. If there are more than 5 missing items then the total score will be missing.

In addition to the total score, behavioral subscales will be defined as follows ([Rabinowitz et al, 2005](#)):

- Aggressive Behavior: 12 Items (minimum = 12, maximum = 84)
- Sum of scores from items 3, 4, 7, 8, 9, 10, 11, 13, 14, 15, 21 and 25
- Physically Non-aggressive Behavior: 6 Items (minimum = 6, maximum = 42)
- Sum of scores from items 1, 2, 16, 22, 26, and 29
- Verbally Agitated Behavior: 4 Items (minimum = 4, maximum = 28)
Sum of scores from items 5, 6, 18, and 19
- Hiding and Hoarding : 2 Items (minimum = 2, maximum =14)
Sum of score from items 23 and 24

For the aggressive behavior subscale, if less than 3 items are missing then the aggressive behavior subscale score will be imputed by replacing the missing item with the mean of the non-missing values (rounded to the nearest integer) for that subject and timepoint within aggressive behavior subscale. If more than 2 items are missing then the aggressive behavior subscale score will be missing.

For the physically non-aggressive subscale, if only 1 item is missing then the physically non-aggressive subscale score will be imputed by replacing the missing item with the mean of the non-missing values (rounded to the nearest integer) for that subject and timepoint within physically non-aggressive subscale. If more than 1 item is missing then the physically non-aggressive subscale score will be missing.

For the verbally agitated behavior and hiding and hoarding subscales, if any of the items are missing then the subscale score will be missing.

5.2.2 Zarit Burden Interview (ZBI)

The ZBI is assessed at Baseline, Weeks 2, 4, 8, 12, 20, 28, 36, 44, and 52/ET visits.

The ZBI was designed to assess the stresses experienced by caregivers of patients with dementia. Caregivers are asked to respond to a series of 22 questions about the impact of the patient’s disabilities on their life. For each item, caregivers are to indicate how often they felt that way (never, rarely, sometimes, quite frequently, or nearly always) (0-4). The total score of ZBI will range from 0 to 88, with higher scores denoting more stresses experienced by caregivers. If there are less than 5 missing items then the total score will be imputed by replacing each missing item with the mean (rounded to the nearest integer) of the non-missing values for that subject and timepoint. If there are more than 4 missing items then the total score will be missing.

If the informant of ZBI is a professional caregiver, their ZBI total scores will not be included in the summaries.

5.2.3 Alzheimer’s Disease Cooperative Study – Activities of Daily Living Inventory (ADCS-ADL)

The ADCS-ADL is assessed at Baseline and Weeks 12, 28 and 52/ET visits.

The ADCS-ADL is an inventory to assess activities of daily living (ADL) in subjects with AD. This is a caregiver-rated 23-item questionnaire, with sub-questions and sub-items for some items, including both basic (e.g. personal hygiene, eating, bathing) and instrumental (e.g. preparing a meal, using a telephone) ADLs. The total score can range from 0 to 78, with lower scores indicating worse functioning.

A response of “DON’T KNOW” is not considered a missing value, rather it will be scored similarly to a “NO” response (i.e., that item score will be set to 0). The following table includes the item score range and the scoring rule. These rules will only apply in the analysis dataset; the raw data values will remain unchanged.

Table 2 ADCS-ADL Item Score Range

Item Number	Score Range	Note*
1-5, 8-12, 14, 17-19, 21, 22	0-3	
For item 8, the score is sum of 8A, 8B, and 8C. The sub-question will be equal to 0 if the main or sub-question checks NO or DON’T KNOW.
 
For item 18, the score is sum of 18A, 18B, and 18C. The sub-question will be equal to 0 if 1) the main or sub-question checks NO or DON’T KNOW; or 2) “patient is institutionalized” box is checked.
 
For item 22, if NO or DON’T KNOW is checked then assign item score = 0. If YES is checked and one or more sub-item is

Item Number	Score Range	Note*
		checked, but the sub-question is not answered, then assign item score = 1. Otherwise, item score is equal to the non-missing sub-question score.
6	0-7	Sum of 6A (0-3; 0 if the main question checks NO or DON'T KNOW) and 6B (0-4).
7	0-5	
13, 15, 16, 23	0-4	For item 16, the score is sum of 16A (0-3; 0 if the main question checks NO or DON'T KNOW) and 16B (0-1; 0 if the main or sub-question checks NO or DON'T KNOW). For item 23, if NO or DON'T KNOW is checked then assign item score = 0. If YES is checked and one or more sub-item is checked, but the sub-question is not answered, then assign item score = 1. Otherwise, item score is equal to the non-missing sub-question score.
20	0-2	

* Item 7-21. If NO or DON'T KNOW is checked, then assign item score = 0. If YES is checked, the score of the item is sum of non-missing score(s) of the sub-question(s).

In addition to the total score, the following subscale scores will be defined:

- Basic subscale score: 6 Items (minimum = 0, maximum = 22)
 Sum of scores from items 1, 2, 3, 4, 5, 6
- Instrumental subscale score: 17 Items (minimum = 0, maximum = 56)
 Sum of scores from items 7, 8, 9, 10, 11, 12, 13, 14, 15, 16, 17, 18, 19, 20, 21, 22, 23

After applying the preceding data handling rules, if missing values remain then the 23-item total, basic, and instrumental scores will be derived as follows:

For the 23-item total score, if the sum of the maximum possible scores among all of the missing items is less than or equal to 16 then the total score will be derived as 78 multiplied by (sum of observed item scores divided by the sum of maximum possible scores among observed items), rounded to the nearest integer. Otherwise, the total score will be missing.

For the basic subscale score, if the sum of the maximum possible scores among the missing items is less than or equal to 4 then the basic subscale score will be derived as 22 multiplied by (sum of observed basic item scores divided by the sum of the maximum possible scores among observed basic item scores), rounded to the nearest integer. If the sum of the maximum possible scores among the missing items is greater than 4 then the basic subscale score will be missing.

For the instrumental subscale score, if the sum of the maximum possible scores among the missing items is less than or equal to 11 then the instrumental subscale score will be derived as 56 multiplied by (sum of observed instrumental item scores divided by sum of the maximum possible scores among observed instrumental item scores), rounded to the nearest integer. If the sum of the maximum possible scores among the missing items is greater than 11 then the instrumental subscale score will be missing.

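### For ADCS-ADL items 8, 16 and 18, a sub-question left blank under a YES scores 0 while the item counts as fully observed, so the error is zero or toward worse function

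*SAP*

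**What the plan says.** SAP 5.2.3 defines the ADCS-ADL as 23 items: "The total score can range from 0 to 78, with lower scores indicating worse functioning". Table 2 then gives item rules. Three of the items numbered 7 to 21 are described as sums of parts: "For item 8, the score is sum of 8A, 8B, and 8C"; "For item 18, the score is sum of 18A, 18B, and 18C"; and "For item 16, the score is sum of 16A (0-3" plus 16B, which runs 0 to 1. The notes for these items list when a part is set to 0: a NO or DON'T KNOW and, for item 18, an institutionalized patient. A blank is not on that list.

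The footnote to Table 2, covering items 7 to 21, settles what happens to blanks once the main question is YES: "If YES is checked, the score of the item is sum of non-missing score(s) of the sub-question(s". It sets no minimum number of answered parts and does no rescaling.

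Proration comes second: "After applying the preceding data handling rules, if missing values remain then the 23-item total, basic, and instrumental scores will be derived as follows". The total is then 78 multiplied by the "sum of observed item scores divided by the sum of maximum possible scores among observed items), rounded to the nearest integer", provided the missing items' maxima add to no more than 16. The instrumental subscale works the same way with 56 and a limit of 11.

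**The concern.** The two steps treat missing content in opposite ways. An item missing altogether is assumed to sit at the subject's average level on the other items. A part missing from an otherwise answered item is assumed to show no function, and because the item now counts as observed, proration does not correct for it.

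This is also out of line with the rest of the SAP. The CMAI total, ZBI, NPI-C domain and MMSE rules fill permitted missing items from the mean of the answered ones. Within the ADCS-ADL, items 22 and 23 get a non-zero default when a sub-item is ticked "but the sub-question is not answered, then assign item score = 1".

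Change from Baseline in ADCS-ADL is the exploratory endpoint that corresponds to the functional-status objective. It is collected only at Baseline and Weeks 12, 28 and 52. A skipped part whose true answer was above 0 lowers that visit's score. After Baseline this adds apparent decline. At Baseline it adds apparent improvement to every later change score.

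**Working it through.** **Inputs.** Item ranges and part structure come from SAP Table 2; proration formulas and limits come from the text after it. That each part of items 8 and 18 runs 0 to 1 is inferred from three parts summing to a 0–3 item. Function levels below are assumptions, since the documents give none. No other item is taken to be missing.

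**Reproducing the plan's maxima.**
- Basic (items 1–6): 5×3 + 7 = 22.
- Instrumental (items 7–23, in order): 5 + 5×3 + 4 + 3 + 4 + 4 + 3×3 + 2 + 3 + 3 + 4 = 56.
- Total: 22 + 56 = 78.

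All three match the SAP.

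**Largest error against the true score, at least one part answered.** Item 8: two blank 1-point parts, 2. Item 16: 16A blank, 3. Item 18: two blank parts, 2. Sum: 7.

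**When does a part-answered item score below a wholly blank one?** Let M be the item maximum, s the sum of its answered parts, R the sum on all other items, and p = R/(78 − M).
- Part-answered, SAP rule: R + s.
- Wholly blank, prorated: 78R/(78 − M) = R + pM.

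Before rounding, part-answered is lower when s < pM:
- Items 8 and 18 (M = 3): s = 0, p > 0; s = 1, p > 0.33; s = 2, p > 0.67.
- Item 16 (M = 4): s = 0, p > 0; s = 1, p > 0.25; s = 2, p > 0.50; s = 3, p > 0.75.

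**Worked records.** The last column keeps the answered parts and drops only the blank parts' maxima from the denominator.

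| Record | SAP rule | Item(s) wholly blank | Blank parts dropped |
|---|---|---|---|
| True total 50; 16A = 2 blank, 16B = 1 | 47 + 1 = 48 | 78×47/74 = 49.5 → 50 | 78×48/75 = 49.9 → 50 |
| True total 50; one part = 1 on each of 8 and 18, only 16B = 1 on 16 | 43 + 3 = 46 | 78×43/68 = 49.3 → 49 | 78×46/71 = 50.5 → 51 |
| True instrumental 30, same pattern | 23 + 3 = 26 | 56×23/46 = 28 | 56×26/49 = 29.7 → 30 |
| True total 78, same pattern | 68 + 3 = 71 | 78×68/68 = 78 | 78×71/71 = 78 |

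**Where the ordering reverses.** With 22 of 75 on the other items and two parts of item 8 answered 1, the SAP rule gives 24 and the blank item 78×22/75 = 22.9 → 23. With 22 of 74 and 16A = 3, 16B blank, the SAP rule gives 25 and the blank item 78×22/74 = 23.2 → 23.

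Enumerating every partial pattern against every possible sum on the other items, unweighted, part-answered is worse, equal or better in 55.5%, 27.6% and 16.9% of cases for items 8 and 18, and in 58.2%, 20.7% and 21.1% for item 16. These shares describe the rule; they do not predict how often it will happen in the trial.

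**The case against.** The strongest defence is that the plan is internally ordered. The SAP applies item rules first and proration afterwards, so a reader who infers that the two rules contradict each other goes too far. Scoring an unaffirmed ability as 0 also resembles the stated DON'T KNOW convention. That stands as a description of the choice, but the SAP itself distinguishes DON'T KNOW from missing and gives no reason to score a blank the same way.

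Three other strong readings are tempting and not supported:
- That a half-answered item always scores worse than a blank one. It does so only when s < pM; low-function subjects with positive answers can score equal or better.
- That proration never reaches items 8, 16 and 18. If the main question is blank, the item is missing and is prorated.
- That any skipped part after Baseline shows as decline. There is no error if the true answer was 0, and none in the change score if the same loss occurred at Baseline.

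Nor does the footnote cover every multi-part item. Item 6 (6A, 6B) lies outside it, and items 22 and 23 have their own rule.

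Several points limit the impact. Protocol 8.1 requires omissions on the eCRF to be explained and monitors to query discrepancies, which should keep blanks few. SAP 5.2 lists raw and derived scores, so affected records can be found. SAP 12 plans no hypothesis test, and the primary endpoint is TEAEs. The questionnaire is not reproduced and the parent study's scoring rules are not visible here, so neither can be checked. All of this bears on size; none of it makes a blank equivalent to no function.

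**Conclusion.** The point holds for items 8, 16 and 18 when YES is checked and some, but not all, parts are blank. The stated rule is biased in one direction: zero error or a lower score, up to 2, 3 and 2 points respectively. The 7-point combined loss requires the maximum loss on all three items at one assessment and is an outer bound. In the illustrative record with a true total of 50, one skipped 16A costs 2 points and three part-answered items cost 4.

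These sizes assume 0–1 parts for items 8 and 18 and no other missing items. The effect on group means cannot be estimated, because the documents give neither the frequency of blanks nor the subjects' level on the scale; it is nil if no sub-question is skipped. No safety conclusion depends on it. It is worth correcting because the bias is avoidable at little cost.

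**What to change.** Amend the Table 2 footnote for items 8, 16 and 18. When YES is checked and some sub-questions are blank, keep the answered scores and remove only the blank sub-questions' maxima from the proration denominator. Count those maxima toward the existing limits of 16 (total) and 11 (instrumental). Leave NO, DON'T KNOW and institutionalized at 0, and leave wholly missing items as now.

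Making the whole item missing is a different rule: 49 against 51 in the three-item record above, where the truth is 50. It discards valid answers, and the three items would use 3 + 4 + 3 = 10 of the 11 instrumental points. Dropping only the blank parts uses 2 + 3 + 2 = 7.

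Apply the same derivation to the ACP-103-032 scores that feed the change-from-Baseline tables, so that both ends of each change are scored alike. The same edit could say what happens when YES is checked with every part blank, and when one part of item 6 is missing, since the SAP does not clearly settle either.

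The cost is a sentence or two of SAP text and a small change to the derivation code, with no new data. A few more records may reach the missing-item limits, and ACP-103-032 values in these tables may differ from that study's own reported scores, which a table footnote should state.
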